2. ADEQUACY OF PROTECTION AGAINST RISKS

a. Recruitment and Informed Consent

The study subject's primary care provider(s) will make first contact on behalf of the study so there is no appearance of a breach in confidentiality. Once a subject has expressed interest in this research study, to obtain informed consent, one of the study coordinators will explain to each subject in lay language the purpose, benefits and risks of the investigation. Consent will be given following an informative discussion period and either by reading the Informed Consent to the subject or by allowing the subject to read the consent, then reviewing it with the subject. All study coordinators have taken the Research Coordinator course and have passed their Miami CITI. Every attempt will be made to conduct this study in full compliance for the protection of the subjects. For those women who are not fluent in English and whose first language is Spanish, a Spanish version of the consent form will be used (translated by BiLingo from IRB approved English consent and submitted as an amendment to IRB). Following the subject's verbal agreement to participate in the study, the subject will sign the informed consent; the study subject. The original informed consents will be placed in locked research file in study coordinators' office, [name]. A copy of the informed consent also will be placed in the subject's study binder (located in locked cabinets at same location). A study coordinator note will be placed in Epic identifying an MUSC woman as participating in a vitamin D and pregnancy RCT.

b. Protection against Risk

All of the investigators have conducted several clinical trials; they are well versed in the issues of patient/subject confidentiality and have completed the Miami CITI course. They are nationally and internationally known in their fields. All study coordinators have completed the Miami CITI and the Research Coordinator course at MUSC. The endeavors of the PI, co-investigators and study coordinators to maintain subject confidentiality will be ensured.

All maternal blood, urine, and vaginal samples as well as infant blood and placental tissue will be labeled with the patient's name and medical record number to ensure proper tracking. Each study subject (and infant) then will be assigned a specific study number without any reference to the woman or infant's name, which will be used to enter all data into the web database. We will follow all HIPAA guidelines to maintain protection of patient/subject information. With these precautions in place, there is a remote risk that the samples and data could be linked to the woman and her infant; however, the study number and the name will be kept in a separate file in the locked offices of the study coordinators. The data will be entered in a secured database with only the study number entered, thus ensuring that the number and data will be kept separately from the woman and infant's names. All this information will be kept confidential, and when reported in scientific journals, the information will not have any identifying information regarding study subjects.

Should any untoward reaction occur, subjects would receive treatment at the Medical University of South Carolina. The study will cover the costs of laboratory tests; however, additional costs of treatment will be the responsibility of the subject as described in the informed consent.

See main section #5 Data Safety and Monitoring Plan that follows for full details; this is a clinical trial. This study meets the guidelines of clinicaltrials.gov as a clinical trial requiring a Data Safety and Monitoring Plan and a Data and Safety Monitoring Committee. Two of the members of the Data and Safety and Monitoring committee are scientists external to MUSC well known in the field of vitamin D metabolism and calcium metabolism. Two of the members are physician scientists external to MUSC, who are also well known in the field of calcium and vitamin D metabolism. A fifth member will be [name], epidemiologist at MUSC with considerable experience serving on the DSMC of other clinical trials. [name] was the chair of the DSMC of the two prior vitamin D supplementation trials conducted by this study team. He will maintain the database of the study, follow HIPAA guidelines, and conduct ongoing interim analyses to ensure that the risk: benefit analyses remain in favor of benefit to the subjects.

3. POTENTIAL BENEFITS OF THE PROPOSED RESEARCH TO THE SUBJECTS AND OTHERS

Pregnant women enrolled in the study may avoid vitamin D deficiency during their pregnancy. The developing fetus may have more normal calcium and vitamin D levels, better bone mineralization, and improved immune function and brain development. Another potential benefit of this study is that data will be generated that will translate into recommendations for optimal vitamin D status during pregnancy. Increasing numbers of Americans are becoming aware of the risks of hypovitaminosis D, and have begun taking supplemental vitamin D. Without monitoring, the potential for overdosing—although small, exists. There needs to be additional controlled trials that will serve as a guide for practitioners and health care policy makers when recommending the DRI for vitamin D during pregnancy in all ethnicities.

The risks to the subjects in participating in this study (phlebotomy, hypercalciuria, hypercalcemia, confidentiality issues) are reasonable for the following reasons: The issue of adequate vitamin D levels in pregnant women and in women in general is a recent public health problem that reflects the vitamin D-poor content of modern diets and markedly decreased sunlight exposure (a relatively new phenomenon in our evolution) that follows the recommendation of the American Cancer Society and the American Dermatological Society. Thus, the issue of maternal supplementation with vitamin D becomes relevant for thousands of women and their developing fetuses. Hypovitaminosis D during pregnancy is a preventable disorder whose occurrence is widely pervasive in the African American community (affects >75% of reproductive age African Americans) with the majority of their neonates being hypovitaminotic *in utero* and at birth. Hypovitaminosis D is also prevalent in the Hispanics (affects approximately 60% of women of reproductive age). Secondly, the maximal dose that women will take for 10-40 weeks gestation is 5-fold lower than the per kg dose given to preterm and term infants routinely in total parenteral nutrition and formulas. Compared to the Masaii tribe in East Africa, who receive 5-9 hours of

sunlight per day and achieve vitamin D levels well above that achieved taking 4000 IU vitamin D₃, day, this supplementation regimen is aimed at reversing the vitamin D deficiency epidemic in the U.S. and other areas of the world. We now know that vitamin D deficiency has far more clinical implications than integrity of the skeleton, including impaired immunity and increased risk of various disease states, including diabetes, neoplasia, and multiple sclerosis. Through vitamin D supplementation during pregnancy, we believe that participation will beneficially improve overall health status of mother and her developing fetus. Because of the close monitoring of the pregnant women and their developing fetuses through pregnancy, we will have minimized the risks of participation in this study. Should a woman develop hypervitaminosis D, hypercalciuria or hypercalcemia, there are appropriate safeguards built into the study to minimize the risk to the mother and her infant.

4. IMPORTANCE OF THE KNOWLEDGE TO BE GAINED

The issue of maternal supplementation with vitamin D becomes relevant for thousands of women and their unborn fetuses due to recent public health information showing that the majority of pregnant women have inadequate vitamin D levels and decreased sunlight exposure. The potential co-morbidities of pregnancy caused by vitamin D insufficiency or deficiency are increasing and occur with more frequency in African-American and Hispanic ethnicities. As shown in our previous vitamin D supplementation pregnancy trials, hypovitaminosis D is a preventable disorder with adequate supplementation; we strongly believe that the DRI for pregnant women, especially darkly pigmented individuals is woefully inadequate. Optimal vitamin D supplementation becomes an issue for the majority of pregnant women in this country and is necessary to decrease health disparities due to ethnicity.

The results of our previous vitamin D supplementation clinical trials in pregnancy did not show any detrimental effects (hypercalcemia or hypercalciuria) of daily intake of 4000 IU of vitamin D (5, 6). While in the NICHD vitamin D supplementation trial, there was a trend toward reduction in co-morbidities of pregnancy (5), in the Thrasher Research Fund trial involving community-based women living at or near the poverty level, there was evidence of reduced preterm labor, preterm birth, and infection as a function of maternal total circulating 25(OH)D levels, effects that persisted even after controlling for race (6). Yet, in both studies where the health status of the mother was not the focus of the trial nor was immune function, these are post-hoc analyses and can only suggest correlation. In the present RCT, we hope to show statistical differences in the co-morbidities, and show improved immune function with improved vitamin D status.

Based on the data of vitamin D supplementation in normal adult men and women of diverse ethnic backgrounds, our previous vitamin D pregnancy and lactation trials, and the current practice of safely supplementing with 5-8 fold higher IU/kg doses in infants and young children, there is little risk of hypervitaminosis D occurring in pregnant subjects enrolled in this study. Rather, it is quite likely that the woman and her fetus (later, infant) will achieve more satisfactory vitamin D and calcium homeostasis that will yield improved immune function and reduction in co-morbidities of pregnancy. Should a woman develop hypervitaminosis D, hypercalciuria or hypercalcemia, there are appropriate safeguards built into the study to minimize the risk to mother and her infant. Thus, the risks to the subjects are reasonable in relation to the importance that reasonably may be expected to result.

5. SUBJECT SAFETY AND MINIMIZING RISKS (Data and Safety Monitoring Plan)

DATA AND SAFETY MONITORING PLAN: The operation of the DSMB is crucial to the safety of the subjects who will be enrolled in the study. Following the recommendations of the DSMB will be an essential and fundamental part of this Research Protocol.

A. **Creation of a Data and Safety Monitoring Board (DSMB)**: This grant application meets NIH policy and Guidelines on the inclusion of a Data and Safety Monitoring Plan for clinical trials mL and

http://grants.nih.gov/grants/guide/notice-files/not98-084.html). MUSC as the Institute and Center (IC) of this grant will have a Data and Safety Monitoring Committee (DMSC) in place as outlined in this grant. Two of the members of the DSMC are scientists external to MUSC well known in the field of vitamin D and calcium metabolism. Two of the members are physician scientists external to MUSC who also are well known in the field of calcium and vitamin D metabolism. A fifth member will be [name], epidemiologist at MUSC with considerable experience serving on the DSMC of other clinical trials (current and completed). He will maintain the database of the study, follow HIPAA guidelines, and conduct ongoing interim analyses to ensure that the risk: benefit analyses remain in favor of benefit to the subjects.

B. Conduct ongoing monitoring of interventional trial by those who have appropriate expertise to accomplish the trial's mission: The MUSC clinical lab is required to notify the PI of any critical lab values. The Study Coordinators will be responsible for checking laboratories of the women within 72 hours of their reporting and then entering the laboratory data into the computer. They will be provided with a set of normative laboratory values as a reference. The Clinical PI will review values during the weekly study meeting or will be notified if a value falls outside of the referent value range. All data will be verified independently by the Data Processing Center under the direction of [name]. The DSMC will be notified via telephone and fax with source documents and adverse report sheets if a subject's value falls outside the referent value range. In addition, all adverse events will be reviewed semiannually by the DSMC, whose report will be forwarded to the Kellogg Foundation on a quarterly basis and the IRB yearly. The Investigators will report all Serious Adverse Events by telephone to the IRB and the DSMC; in addition, the IRB, the DSMC, and Kellogg Foundation will receive a written report within 10 days of the Clinical Investigators' knowledge of the Event. In addition, the investigators will generate a quarterly report to the DSMC regarding subject enrollment, subject completion, adverse events and serious adverse events. The DSMC will review the report and a summary letter with their findings sent to the IRB.

C. Interim Data Analyses & Monitoring: Interim analyses for the evaluation of safety and efficacy will be conducted based on the recommendations of the Data Safety & Monitoring Board. The DSMC will serve to monitor for safety and efficacy. DSMB reports produced by [name] team will include summary statistics: on mother recruitment (expected vs. actual), data form quality (completion and timeliness of forms); tracking of data editing; demographics of the randomized mothers; aggregate safety; aggregate efficacy; and related information. The DSMB also will monitor the trial from the standpoint of futility using the techniques of Lan and Wittes (119).

F. REFERENCES/LITERATURE CITATIONS

Describe the facilities available for this project including laboratories, clinical resources, etc. Study subjects will be seen in obstetrical clinics at MUSC; interested pregnant women not being followed at any of these clinics can consent for the study and be seen in the CTRC at MUSC. Research laboratories will include several in the Children's Research Institute – [name]/[name], [name] and [name] as well as several in Obstetrics and Gynecology – [name] and [name]/[name], and laboratories of [name] and [name] at MUSC. The laboratory of [name] is located in the Department of Environmental Health Sciences, University of South Carolina.

I. INVESTIGATOR BROCHURE

If applicable, attach the electronic version of the investigator brochure. Go to the application under "additional uploads" to attach this information.

n/a

J. APPENDIX

Attach any additional information pertinent to the application, such as surveys or questionnaires, diaries or logs, etc. Go to the application under "additional uploads" to attach this information.

Relevant Papers:

Preventing Health Disparities during Pregnancy through Vitamin D Supplementation

NCT#01932788

11/6/2013

Statistical Analysis: The primary analysis in this investigation will compare levels of maternal 25(OH)D across the two supplementation groups as 'Intention-to-Treat' and will employ Mantel-Haenszel mean scores; however, a 'Per Protocol' (oversampling to consider attrition) analysis also will be done. This two-step analysis provides information regarding the efficacy of these dosage levels in increasing vitamin D and the effectiveness of oral supplementation to increase vitamin D. Whether the losses are random or are biased with respect to ethnicity, or supplementation arm will be tested. Any differential losses will be reported and examined with the use of propensity scores.

Because of the unique nature of the contributions of potential confounders, two approaches to the analysis will be employed. The first and primary analysis will use a Mantel-Haenszel estimate of the mean treatment difference, computed from stratum-specific treatment differences, which will utilize a weighted average of treatment differences across ethnicity. Mean differences will be calculated for the experimental dosage relative to the 400 IU group. Bonferroni adjustments will be made for the Type I per comparison error rates to correct for multiple testing. The treatment differences, estimated variances, and confidence intervals for the differences will be estimated for maternal serum 25(OH)D. This mode of analysis is quite effective in clinical trials as it is less dependent on normal theory assumptions and associated assumptions such as homogeneity of variance. Parametric models also will be fit, but the primary analysis will rest on Mantel-Haenszel mean scores techniques readily done within SAS. Parametric dose response curves also will be generated to describe the relationship between 25 (OH)D and dosage.

The proportion of participants who completed the daily supplement regimen will be estimated, with a similar "per protocol" style analysis restricted to those individuals. Finally, techniques of multiple linear regression will be employed to describe the interactive effects of ethnicity, as well as the effects of other covariates, such as seasonality, mother's age and fecundity, on baseline serum 25(OH)D. These models will be assessed for violations of the model assumptions, and corrected for such violations as appropriate.

The second statistical approach measures the effects of the confounders and takes the more traditional approach of assuming normal distribution for Vitamin D, and will be performed in parallel fashion to compare treatment effects in 400 IU and 4400 IU vitamin D groups. The primary research aim is to determine if supplementation is associated with an increase in vitamin D concentrations. As discussed below, it will be necessary to identify and control for other factors (confounders) that may also be associated with changes in vitamin D levels.

Paired analyses according to the study plan will be conducted by employing McNemar chisquare for categorical variables, paired t-tests for normally distributed variables, repeated measures ANOVA for longitudinal analyses, and multiple linear regression for multi-variable analyses to control for confounding. Correlation will be used to assess the linear association between outcomes and those factors expected of an accumulated dose-response relationship (e.g., sunlight exposure), and individual regression tests to identify the strength of the association between outcomes and each characteristic. The resulting coefficients then will be translated into a formula for the linear association between each factor and outcomes. In the event that there are non-linear distributions, appropriate data transformations will occur as necessary.

Both groups will be compared for differences in any factors at baseline, and will include: information contained in the maternal sociodemographic, maternal pregnancy and delivery, and maternal calcium, creatinine, vitamin D₃, 25(OH)D, and urinary calcium creatinine ratio. While the stratified blocked randomization technique should minimize the potential for baseline differences, this first step will confirm whether there should be adjustment for any initial differences in follow-up analyses. Next, differences between baseline and follow-up will be examined for those variables that may have changed over the follow-up period (health assessment; physical activity; and blood and urine outcome measures) to identify those factors that may serve as confounders or effect modifiers for the vitamin D assessments. The potential influence of identified confounders or interaction terms will have to be considered for any change in vitamin D status.

Changes in vitamin D outcomes will be compared between treatment arms with the additional information from sunlight exposure, pigmentation/melanin index, maternal physical activity assessment, maternal dietary history, health, and medication questionnaires. This detail will allow the separation of changes in vitamin D parameters as a function of confounding factors from supplementation. The study is powered to explore the degree to which changes in vitamin D parameters are a function of supplementation and ethnicity. To assess whether there are differences in the slopes or linear dissimilarities in the outcomes over time, repeated measures techniques will be used to compare longitudinal changes in outcomes between groups. This technique also provides a graphical depiction of the slopes over time and can identify if there are linear or plateau responses to differences in vitamin D supplementation concentration; it also will allow determination of data transformation techniques required for subsequent analyses if the slopes over time are non-linear.

The final step in the second statistical approach will determine whether potential group differences in the various outcomes are a function of any of the potential confounders—with particular attention to skin pigmentation and sunlight exposure. This step will identify changes in outcomes associated with population factors independent of the group (supplementation) assignment. The extent of more complex statistical analyses will be predicated on the number of individuals comprising specific strata, and thus, restricted by a reduction in the statistical power. Such comparisons will be reported as information for future studies. To clarify, using sunlight exposure as a representative example, the independent effect of vitamin D supplementation may be found to have been modified by the amount of sunlight exposure. As such, the changes in outcomes attributable to each factor, independently, and then when considered in combination will be partitioned. While the major goal of this study is to examine the various outcomes as an independent function of vitamin D supplementation—thereby controlling for all other group differences, the changes in outcomes that are associated with these group differences will be examined and reported in detail. In this way, the changes in vitamin D that are associated with each factor independently will be partitioned.

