(21) Maternal Baseline and Monthly Vitamin D and Calcium Homeostatic Parameters: A 14 mL sample of whole blood will be drawn from the mother at the scheduled obstetrical visit monthly as well as at delivery and placed in an SST tube to be processed in the CTRC Clinical Laboratory for serum separation. The serum will be placed in a -80°C freezer and sent to [name] laboratory on dry ice. Each serum sample will be analyzed for maternal circulating levels of total 25(OH)D, 1,25(OH)₂D, iPTH (5), batched for serum cytokine analysis, and batched for measurement of megalin and cubulin. 25(OH)D will be run on all subjects after 3 months supplementation. Mothers who are still frankly vitamin D deficient (less than 15 ng/ml) will be placed on open label vitamin D gummies for the remainder of their pregnancy.

(22) Monthly Maternal Urine Sample: A random urine sample will be obtained from the mother at each obstetrical visit to be sent to the Clinical Chemistry Laboratory for urinary Ca and creatinine measurement and derivation of the urinary Ca: creatinine ratio. This ratio will be used as an indicator of hypercalciuria that precedes hypercalcemia. Results of these urine studies will be reported directly to [name]. An additional aliquot of the urine sample will be frozen for future cytokine analysis.

(23) Cord Blood Vitamin D and Calcium Measurements. At the time of delivery, 10-mL of whole blood will be drawn from the umbilical vein then sent to the CTRC Clinical Laboratory facility for processing. One red bullet (0.5 cc aliquot) will be sent to the Clinical Chemistry laboratory for measurement of total calcium and creatinine. The remaining blood will be processed in the CTRC Clinical Laboratory immediately for serum separation and placed in a -80° C freezer then transported on dry ice to [name] laboratory for later determination of each neonate's circulating levels (at the time of delivery) of intact iPTH, total 25(OH)D, and 1,25(OH)₂D (5). Additional frozen serum will be batched for analysis of cytokines. Every effort will be made to collect cord blood at the time of delivery. An additional 15 mL plasma sample will be obtained from the cord for immune privilege flow cytometry studies.

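### The primary 25(OH)D comparison adjusts for ethnicity only and leaves out baseline 25(OH)D, which is already measured: a free gain in precision, not a bias

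*SAP*

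**What the plan says.** The first approach in the SAP's Statistical Analysis section "will compare levels of maternal 25(OH)D across the two supplementation groups". Its estimator is a Mantel-Haenszel mean difference "computed from stratum-specific treatment differences, which will utilize a weighted average of treatment differences across ethnicity". Parametric models are to be fitted as well, but the primary conclusion rests on the Mantel-Haenszel result. Within that approach, baseline 25(OH)D appears only as the outcome of a descriptive regression on ethnicity, season and maternal characteristics ("age and fecundity, on baseline serum 25(OH)D").

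The baseline value exists. Protocol section D(21), "Maternal Baseline and Monthly Vitamin D and Calcium Homeostatic Parameters", plans serum 25(OH)D at baseline, monthly and at delivery.

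The second statistical approach uses baseline in two ways:
- It compares the arms on baseline factors, 25(OH)D among them, and says "this first step will confirm whether there should be adjustment for any initial differences in follow-up analyses".
- It works with changes and repeated measures: "Changes in vitamin D outcomes will be compared between treatment arms with the additional information from sunlight exposure". It adds: "The study is powered to explore the degree to which changes in vitamin D parameters are a function of supplementation and ethnicity".

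The second approach also looks for confounders among follow-up data: "Next, differences between baseline and follow-up will be examined for those variables that may have changed over the follow-up period". The variables listed are the health assessment, physical activity, and the blood and urine outcomes.

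**The concern.** A woman's 25(OH)D at entry is likely to predict her later value within her ethnic group. Stratifying by ethnicity removes the variation between groups but not the variation between women in the same group. Leaving baseline out therefore puts explainable variation into the standard error.

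The conditional rule in the second approach is not a good substitute. Under randomisation any baseline difference between arms is due to chance, and the value of adjustment depends on how strongly baseline predicts outcome, not on whether the arms happen to differ. Change scores do use baseline, but less efficiently than a covariate does.

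At stake are the width of the primary confidence interval and the resolution of the supplementation-by-ethnicity contrasts, which are central to a trial about disparities.

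The secondary point is of another kind. If a variable measured after randomisation is itself affected by supplementation, adjusting for it removes part of the effect being estimated.

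**Working it through.** **The plan's own figure.** Protocol section E(1) asks for 300 completers, half of each ethnic group in each arm: 150 per arm, and 50 per arm per group. No alpha, power, effect size or SD is given, so 300 cannot be reproduced. What follows uses only the 150 and the 50.

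**Inputs**
- SD about 13 ng/mL. Protocol section C gives SDs of change of 13.2 and 12.9 in an earlier trial. The SD of the follow-up level is not given.
- r, the within-ethnicity correlation of baseline with follow-up, is not in the documents. Assumed: 0.3 to 0.6.
- One follow-up value, with equal variance at baseline and follow-up (assumed). If r = 0.5, SD of change = SD of level × √(2(1 − r)) = SD of level, so 13 can stand for either. At other r, rely on the ratios.

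**Formulas**
- Unadjusted level: SE = SD × √(2/150) = 13 × 0.1155 = 1.50.
- Baseline as covariate: SE × √(1 − r²), so the variance ratio is 1 − r².
- Covariate against change score: variance ratio (1 + r)/2.

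| r | variance cut vs unadjusted level | variance cut vs change score | SE, SD 13 | 95% CI half-width | 300 women worth |
|---|---|---|---|---|---|
| none | – | – | 1.50 | 2.94 | 300 |
| 0.3 | 9% | 35% | 1.43 | 2.81 | 330 |
| 0.4 | 16% | 30% | 1.38 | 2.70 | 357 |
| 0.5 | 25% | 25% | 1.30 | 2.55 | 400 |
| 0.6 | 36% | 20% | 1.20 | 2.35 | 469 |

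The last column is 300/(1 − r²). At r = 0.5 the half-width goes from 2.26 to 1.96 if the SD is 10, and from 3.62 to 3.14 if it is 16.

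**Bias check.** In 4,000 simulated trials per correlation, with three ethnic strata and a true difference of 12 ng/mL, the unadjusted and baseline-adjusted estimates both averaged 11.99 to 12.02. The variance ratio was 0.93, 0.72 and 0.50 at r = 0.3, 0.5 and 0.7, against 0.91, 0.75 and 0.51 by formula.

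**Within one ethnic group.** SE = 13 × √(2/50) = 2.60, half-width 5.10. With the covariate the half-width is 4.86 at r = 0.3 and 4.41 at r = 0.5.

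**Difference in effect between two ethnic groups, repeated measures.** Assume k follow-up values averaged, compound symmetry, r = 0.5, SD 13. Variance per woman, in units of SD²:
- mean change: (1 + (k − 1)r)/k + 1 − 2r = 0.667 (k = 3), 0.583 (k = 6)
- mean with baseline as covariate: (1 + (k − 1)r)/k − r² = 0.417, 0.333

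Multiplying the square root by 13 × √(4/50) × 2.80 (80% power, two-sided 5%) gives a detectable difference of 8.4 to 7.9 ng/mL for changes and about 6.7 to 6.0 with the covariate.

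**Secondary point.** If a follow-up variable is driven linearly by 25(OH)D with within-arm correlation ρ, adjusting for it multiplies the supplementation effect by 1 − ρ². At assumed ρ of 0.1, 0.3 and 0.5 the effect is understated by 1, 9 and 25%. No such ρ is in the documents.

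**The case against.** The plan's choice is defensible. The SAP explains that it prefers an estimator that leans little on normal theory and is easy to run, and the result is unbiased. With SD 13, 150 per arm already detects (1.96 + 0.84) × 1.50 = 4.2 ng/mL with 80% power at a two-sided 5% level. The earlier trial in Protocol section C saw a mean rise of 15.2 ng/mL on 4000 IU, and section B calls the effect of 400 IU minimal. All of this stands, and it is why the point is an improvement and not the correction of an error.

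The size of the gain is assumed. At r = 0.3 it is 9% of the variance, about 5% of the SE. Two features could change both r and the arm contrast: open-label vitamin D for women still below 15 ng/mL after three months (Protocol D(21)), and the universal screening and supplementation at the institution from September 2015 (Protocol D, Activity #7). The earlier trial also had no 400 IU arm. So neither a 15 ng/mL difference nor a completely safe overall test can be taken for granted.

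It is also fair to say that the second approach does use baseline, and that its repeated measures recover some precision. The calculation above shows that the covariate still helps there. The SAP states no significance threshold for its baseline comparison, so how often it would lead to adjustment cannot be computed.

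On the secondary point, the SAP says that the influence of screened factors must be considered, not that each enters a treatment model. It names no particular analyte for adjustment. The factors it stresses most, sunlight and pigmentation, are unlikely consequences of blinded supplementation.

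**Conclusion.** The omission is real and confined to the primary analysis. Prespecifying baseline 25(OH)D would lower the variance of the arm difference at one follow-up by 9 to 36% for assumed r of 0.3 to 0.6; at r = 0.5 and SD 13 the SE falls from 1.50 to 1.30 ng/mL. The ratios do not depend on the SD but do depend on r, which the documents do not give. The overall test is unlikely to change.

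A reader might infer that the primary estimate is biased or underpowered. The documents do not support that: randomisation within ethnicity protects the comparison, and nothing shows a lack of power for the overall difference. The statement assumes that losses, planned at 30%, do not themselves distort the comparison; the SAP plans to examine them.

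A reader might also infer that the second approach will give biased effects. That is possible but not shown. The text admits follow-up blood and urine results as candidate confounders, without saying which would be adjusted for, and the primary estimate is not exposed.

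**What to change.** 1. Name baseline 25(OH)D in advance as a covariate in the primary analysis, for example by stratified randomisation-based ANCOVA with ethnicity as stratum. This keeps the distribution-free Mantel-Haenszel framework.
2. Use the same covariate in the repeated-measures contrasts of supplementation by ethnicity.
3. Keep the comparison of the arms at baseline as description, not as the trigger for adjustment.
4. In the second approach, limit covariates in treatment-effect models to a fixed list of pre-randomisation values, and label any model with follow-up variables as exploratory.

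The cost is SAP wording; no new data are needed. The downsides are slightly more analysis work, an estimate a little harder to explain than a plain stratified difference, and the need to state a rule for women with no baseline value.
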